## 8.2 General procedures

### 8.2.1 Informed consent

The researcher or designated person (qualified and trained) will carry out the informed consent process, obtaining the documented consent of each potential participant prior to their participation in the study, in accordance with institutional procedure P-INV-03: Informed Consent for Clinical Research.

Consent will be documented on a specific research form, in a version approved by the Research Ethics Committee (REC), dated and signed by the participant,

Product: 910002

witnesses, and the person in charge of the consent process. A copy of the document will be given to the participant.

In the event of any modification or additional information, the new version will be submitted for verification and endorsement by the IRB. If this information is relevant to the participant's decision to continue in the study, it must be communicated to them in a timely manner. The process will be documented using a modified informed consent form, a copy of which will be given to the participant.

The delivery of the copy of the form will be documented in an institutional document (F-INV-05: Proof of Delivery of Informed Consent) in which the study identification, research participant data, and signature of receipt of the consent copy will be recorded.

Two moments are defined for the informed consent process: a consent document for the screening process and another for the participant's effective inclusion in the research.

#### 8.2.2 Verification of inclusion/exclusion criteria

The investigator or designated qualified and trained person will review the selection criteria to ensure that the participant meets the inclusion criteria and does not meet any of the exclusion criteria so that the participant can be included in the study and proceed with randomization and the initial visit.

#### 8.2.3 Participant identification card

All participants will receive a "Participant Identification Card" document that will identify them as participants in the research study. This document will contain:

- Research Center Information
- Unique treatment number (included after randomization)

The investigator or designated person will provide instructions for using the card, which must be carried by the participant at all times and presented in case of an emergency or health service requirement.

#### 8.2.4 Medical history assessment

During the selection process, the investigator or designated person qualified and trained in research must obtain and record medical history for evaluation and analysis.

#### 8.2.5 Review of previous and concomitant medications

The investigator or designated person qualified and trained in the research will verify the use of medications (prescribed or not) used during the 30 days preceding

Product: 910002

randomization. All medications that the participant is using at the time of selection will also be recorded.

#### 8.2.6 Assignment of selection number

All participants who have given their written informed consent for the screening process will be assigned a unique selection number that will be used to identify them during the procedures to be performed prior to randomization. These numbers are unique and will not be reused for other participants during the study.

#### 8.2.7 Treatment number assignment/randomization

After the screening phase and following the assignment of selection numbers, the centralized randomization process will be carried out by the person assigned by the research center, trained and qualified for this purpose, and the randomization number will be delivered and treatment assignment will be carried out.

#### 8.2.8 Treatment administration

During the initial visit, the research pharmacist will deliver a masked box according to the participant's treatment assignment. The first study dose, corresponding to day 1, will be administered at the research center, at which time instructions will be given for home use for the following days, during which the participant will self-administer the medications.

The instructions given during the initial and follow-up visits, based on the information provided by the research pharmacist, will focus on three items:

- **Schedules:** Medications should be taken at approximately the same time every day (each participant's medication-taking habits will be evaluated so that the instructions encourage adherence to treatment based on lifestyle). Medications should not be chewed, crushed, or divided; they should preferably be taken with water and on an empty stomach.
- **Missed doses:** If the participant misses/forgets a dose of medication, despite reminder strategies, they should take the missed dose as soon as possible on the same day. If more than 12 hours have passed since the scheduled time, they should wait until the next dose and take a regular dose. They should not take extra medication to make up for the missed dose.
- **Storage:** Medications should be stored in a cool, dry place (below 30°C), protected from direct light, and kept in a tightly closed container.

Product: 910002

### 8.3 Blood pressure measurement

Blood pressure readings will be taken by the researcher or a designated person qualified and trained in the study during the initial, follow-up, and final visits defined in the research schedule. DBP and SBP will be taken during each visit, with the patient seated, on the left arm, following WHO recommendations and using Korotkoff sounds.

Participants will be asked to measure and record their blood pressure at home during the study period using the calibrated digital blood pressure monitor provided by the researcher, following these recommendations for taking measurements:

- Take measurements on the left arm with the blood pressure monitor provided by the researcher.
- Sit in a comfortable chair for three to five minutes with the upper arm at heart level before taking a measurement.
- Do not exercise or engage in any other activity that requires cardiovascular effort prior to taking the measurement.
- Do not eat immediately before the reading, avoid consuming energy drinks such as coffee, tea, or soda.
- Take three readings at intervals of 1 to 2 minutes.
- Take the measurement once a day, at a time when you are not under stress, preferably when you wake up.
- Record the measurements in the blood pressure diary provided by the study.

### 8.4 Follow-up visits

The follow-up process will be carried out through visits every 4 weeks for each drug studied (according to the 2x2 sequence). At visit 2, at the end of week 8, the study drug will be switched (group switch) and weeks 9 and 10 will be identified as a statistical silence period. At the end of week 10, follow-up visit 3 will be conducted, in which the baseline conditions for medication B will be identified according to sequence, and follow-up visits 4 and 5 will then be conducted.

During these visits, efficacy and safety will be evaluated based on physical assessment, laboratory results, and safety reports identified and/or followed up during the consultation.

To encourage adherence to the clinical study, the sponsor will offer gifts to participants, such as notebooks, pens, cups, thermal blankets, briefcases, gym vouchers, healthy cooking courses, and lifestyle courses.

#### 8.4.1 Withdrawal/discontinuation

If the participant decides to discontinue treatment and withdraw from the study, the investigator must carry out all activities required for the early discontinuation visit, performing the corresponding medical assessment and follow-up of all adverse events present at the time of withdrawal. All activities will be documented

Product: 910002

by the principal investigator in the research medical record and corresponding CRF. In addition, the event reporting process will be followed as appropriate (P-INV-02 Reporting of Adverse Events and Serious Adverse Events in Research).

#### 8.4.2 Unblinding in clinical research

In the event of an emergency situation in which the investigator or delegate needs to identify the treatment assigned to the participant, the established institutional procedure will be followed (P-INV-12: Unblinding). The treating physician may request immediate medical information about the patient in the event of a medical emergency in order to optimize clinical management. The investigator will review the physician's request and, if the clinical decision takes a different course of action based on the results, unblinding will be permitted.

The principal investigator will immediately notify the sponsor and proceed with communicating with the person responsible for randomization at the research center to perform the unblinding.

The entire process will be documented in the corresponding medical record, describing the circumstances surrounding the unblinding (date, reason, and person requesting and performing the unblinding), and notification of the report will be sent to the Ethics Committee by the principal investigator or study coordinator.

#### 8.5 Efficacy assessments

Blood pressure control will be assessed at all visits from selection to the final visit. To assess the efficacy of the medication, blood pressure will be measured using a control criterion of SBP/DBP below 140/90 mmHg.

At each check-up, blood pressure and vital signs, weight, and height will be assessed, and laboratory tests will be requested at the beginning of the study and at the end of each cycle, in accordance with guidelines for monitoring patients diagnosed with high blood pressure.

##### 8.5.1 Physical examination

A complete physical examination will be performed at the initial, follow-up, and final medical visits (inspection, palpation, auscultation, and percussion). The investigator may request a specific physical examination if the participant presents any symptoms.

##### 8.5.2 Weight and height assessment

The patient's weight and height should be assessed at the start of the study and at the end of each cycle.

##### 8.5.3 Vital signs

Vital signs will be checked at the initial, follow-up, and final visits. These include

measurement of heart rate, respiratory rate, body temperature, and body weight.

Product: 910002  
(preferably oral).

#### 8.5.4 Electrocardiogram

Twelve-lead ECGs will be performed at the start and end of each cycle. They will be interpreted at the research center by the investigator.

#### 8.5.5 Adverse event monitoring

Adverse event monitoring will include the collection of all AEs and SAEs identified from the signing of the informed consent form until the closing visit.

#### 8.5.6 Clinical laboratory evaluation

Clinical laboratory tests will be performed during screening and at the baseline, follow-up at the end of each cycle, and closing visits (see Appendix 2).

The investigator will review the results, record the data, and document all clinically significant changes identified. All laboratory tests will be performed according to the institution's defined operating procedures.

If laboratory results with abnormal values considered clinically significant are identified, the necessary repetitions must be performed to follow up until normalization or return to baseline values.

### 8.6 Treatment of overdose (25,26)

#### 8.6.1 Symptoms

Symptoms associated with severe nifedipine poisoning are defined as: Altered consciousness to the point of coma, decreased blood pressure, tachycardia, bradycardia, hyperglycemia, metabolic acidosis, hypoxia, cardiogenic shock with pulmonary edema.

#### 8.6.2 Treatment

Priority should be given to eliminating nifedipine and restoring stable cardiovascular conditions. Elimination should be as complete as possible, including from the small intestine, to prevent further absorption of the active ingredient.

The following indications should be considered:

- i. Use of activated charcoal (50 g for adults) if the patient presents within one hour of ingesting a potentially toxic amount. Although it may seem reasonable to assume that delayed administration of activated charcoal may be beneficial for sustained-release (SR, MR) preparations, there is no evidence to support this.
- ii. Alternatively, consider gastric lavage in adults within one hour of a potentially fatal overdose.

Product: 910002

- iii. Consider additional doses of activated charcoal every 4 hours if a clinically significant amount of a sustained-release preparation with a single dose of an osmotic laxative has been ingested.
- iv. Asymptomatic patients should be observed for at least 4 hours after ingestion and for 12 hours if a sustained-release preparation has been taken.

Hypotension resulting from cardiogenic shock and arterial vasodilation may be treated with calcium (10-20 mL of a 10% calcium gluconate solution administered intravenously over 5-10 minutes). If the effects are inadequate, treatment may be continued with ECG monitoring. If an insufficient increase in blood pressure is achieved with calcium, vasoconstrictive sympathomimetics such as dopamine or norepinephrine should be administered. The dose of these drugs should be determined by the patient's response.

Symptomatic bradycardia may be treated with atropine, beta-sympathomimetics, or a temporary cardiac pacemaker, as necessary.

Additional fluids should be administered with caution to avoid cardiac overload.

#### 8.6.3 Adverse events, serious adverse events, and other safety events requiring notification

AEs, SAEs, and other safety events requiring notification shall be reported by the participant to the investigator and/or designated, qualified, and trained personnel during medical visits and/or follow-up calls. The investigator and designated personnel are responsible for detecting, evaluating, documenting, and reporting events that meet the definitions of AEs, SAEs, and other safety events requiring reporting.

The definitions of adverse event (AE) and serious adverse event (SAE), as well as the processes and formats for recording and reporting, are described in Appendix 3. All serious and non-serious adverse events are defined as events of clinical interest (ECI).

#### 8.6.4 Time period, frequency, and method for obtaining information on AEs, SAEs, and other safety events that require notification and follow-up

- I. The collection of information on AEs, SAEs, and other reportable safety events is defined from the signing of the informed consent form and assignment of treatment to the closing visit and will be reported by the investigator.
- II. The preferred method for obtaining information on AEs is oral questioning of the participant, using open-ended, non-leading questions to avoid any bias in the detection of AEs/SAEs/other safety events.
- III. Once the initial notification of AE/SAE/other safety events has been made, the

Product: 910002

investigator will be responsible for following up with each participant through visits and phone calls. Safety events requiring notification must be followed up until resolution, stabilization, or identification of another explanation. It is essential that the investigator follow up on all events to determine their outcome.

#### 8.6.5 Regulatory reporting requirements for SAEs

Legal and ethical obligations will be fulfilled by IMMEDIATE notification of SAEs (within 24 hours) by the investigator to the sponsor.

The sponsor has a legal responsibility to notify the relevant local regulatory authority of safety events related to the study treatment.

All adverse events will be reported to the regulatory authority, IRB, and investigators following the guidelines established in applicable legislation and regulations (E6[R1]-ICH; F-INV-22: Reporting and Follow-up of Adverse Events in Clinical Research).

Unexpected serious adverse reactions must be reported in a safety report prepared by the investigator in accordance with regulatory requirements and sponsor policy.

#### 8.6.6 Events related to the disease and/or disease-related outcomes not classifiable as AEs or SAEs

Events that cannot be classified as AEs or SAEs should be collected throughout the study period. Events that constitute efficacy evaluation criteria will be evaluated by determining severity and causality.

#### 8.6.7 Pregnancy and exposure during breastfeeding

Pregnancy and breastfeeding are not considered adverse events; however, they are grounds for exclusion from the study. Upon spontaneous communication to the investigator or identification of pregnancy by a test performed during follow-up, the sponsor shall be notified.

Reported cases will be followed up until completion, identifying the outcome (full-term pregnancy, termination, etc.).

### 9 Statistical analysis plan

The statistical analysis procedures and strategies proposed for the research protocol are presented below. Any modifications related to the evaluation criteria or analysis methods proposed during the course of the study and before unblinding will be submitted as an amendment to the protocol for approval by the IRB. If the modification is proposed after the study has been completed and before unblinding, it will be mentioned in the clinical study report identified as a complementary statistical analysis.

#### 9.1 Summary of statistical analysis plan

Product: 910002

Design	Phase III, randomized, active-controlled clinical trial to evaluate the efficacy and safety of Nifedipine 30 mg extended-release in adult patients diagnosed with mild or moderate hypertension in Colombia.
Randomization	Permuted blocks, 1:1 ratio
Blinding	Double-blind
Analysis population	Efficacy assessment: Intention-to-treat (ITT) analysis Safety assessment: Analysis of patients treated (ASaT)
Criteria for Primary	Criteria
Secondary of assessment	Proportion of patients achieving the blood pressure control target (<140/90 mmHg) at week 4 of follow-up.  Proportion of patients experiencing serious and non-serious adverse events at week 8 of follow-up.
Statistical methods for efficacy analysis	Difference in mean SBP and DBP from baseline to weeks 4 and 8  Significance value and 95% CI for difference in mean SBP and DBP from baseline to 4 and 8 weeks between the two treatments (repeated measures ANOVA).  p-value or significance value and 95% CI for differences between the proportions of normal blood pressure readings (<140/90 mmHg) at 4 and 8 weeks between treatments using McNemar's chi-square test for differences in proportions with and without continuity correction or Fisher's exact test for paired designs (expected values < 5).
Statistical methods for safety analysis	Percentage of serious and non-serious adverse events between treatments and percentage by type of adverse event for each treatment (descriptive).
Size and power of the sample	A sample size of 50 patients is defined, each patient = 2 study subjects.

Product: 910002

For a maximum change of 3 mmHg between the two treatments, with 90% power, 95% reliability, and 10% losses, a 1:1 ratio, and a sample size of 50:50 (1 patient = 2 study subjects).

## 9.2 Responsibility for analysis/internal blinding

The statistical analysis proposed for this study will be the responsibility of the center's research biostatistician. Blinding will be maintained until the data have been declared final and complete, i.e., after medical/scientific evaluation and identification of protocol deviations.

## 9.3 Endpoints for analysis

### 9.3.1 Efficacy evaluation criteria

The primary efficacy endpoint will be the proportion of participants who achieve blood pressure control, i.e., below the threshold of 140/90 mmHg at week 8 of follow-up.

### 9.3.2 Safety evaluation criteria

The following are defined as safety evaluation criteria:

- Proportion of participants who experience a drug-related adverse event during the study period
- Proportion of participants who experience a SERIOUS adverse event related to the drug during the study period
- Proportion of participants experiencing an adverse event
- Proportion of participants experiencing a SERIOUS adverse event

Adverse events will be recorded until the final visit in weeks 19-20 of the study.

## 9.4 Populations for analysis

### 9.4.1 Population for efficacy analysis

The total randomized population will be analyzed for the efficacy analysis (Intention-to-Treat-ITT). Additionally, a per-protocol (PP) analysis is proposed as a complementary analysis, in which the population is analyzed excluding participants with identified significant protocol deviations that could significantly affect the efficacy assessment, specifically, non-compliance in drug administration (non-adherence to treatment identified in follow-up visits by counting units and recording in a diary).

Product: 910002

#### 9.4.2 Population for safety analysis

The total randomized population that received at least one dose of study treatment (*All-Subjects-as-Treated* - AsaT) will be analyzed.

### 9.5 Statistical methods

#### 9.5.1 Statistical methods for efficacy analysis

##### 9.5.1.1 Primary efficacy analysis

The difference in means and **95% CI** for **SBP and DBP** between the two treatments will be evaluated before and after the intervention at 4 and 8 months, using a fixed-effects repeated measures ANOVA and a Grizzle mixed linear model ANOVA for two crossover periods to adjust for possible carryover effects. The normality of SBP and DBP will be evaluated beforehand at baseline and at 4 and 8 weeks using the Shapiro-Wilk normality test.

The differences in the proportions of subjects with normal blood pressure readings (SBP < 140 or DBP < 90) at 4 and 8 weeks will be evaluated using McNemar's chi-square test for differences in proportions with and without continuity correction or Fisher's exact test for paired designs (expected values < 5).

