### 3.1 Primary objective

- To evaluate the efficacy of Richmond Extended-Release Nifedipine 30 mg versus Extended-Release Nifedipine 30 mg, a comparator currently registered in Colombia, as measured by the proportion of patients with blood pressure control in adult patients diagnosed with mild or moderate hypertension at week 8 of follow-up.

*Endpoint:* Blood pressure control (SBP/DBP) at 8 weeks of follow-up

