## 4 Study design

- Randomized, controlled, 2x2 crossover, phase III, non-inferiority clinical trial to evaluate the efficacy and safety of Nifedipine 30mg extended release Richmond via oral administration VS. Comparator via oral administration, in patients with primary hypertension, at a referral clinic in the city of Bogotá.

[figure not shown]
Target population: Patients with hypertension with normal blood pressure readings (SBP < 140 mmHg or DBP < 90 mmHg)

Source of subjects: Subjects participating in the study will be selected in doctors' offices, medication delivery points, and the community at large. After explaining the study to be conducted, its risks and benefits, verifying the inclusion and exclusion criteria, performing a medical evaluation, reviewing the results of screening studies, and obtaining informed consent.

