#### Sample size.

The sample size was estimated for the non-inferiority crossover study.

When comparing Richmond oral VS. oral comparator, in patients diagnosed with mild or moderate hypertension, who entered the study baseline with controlled blood pressure readings (SBP < 140 or DBP < 90 mmHg), where a maximum change of 3.0 mmHg was taken as the maximum level of change between the two treatments in SBP and DBP, for the hypothesis of non-inferiority in blood pressure control, to an alternative tail taking a 2.5% significance level with 90% power, with a standard deviation of the difference in means of 6 mmHg, the sample size is n=44 pairs (88 subjects in 44 patients) and with a 10% loss adjustment of 50 pairs (100 subjects in 50 patients), with a 1:1 ratio.

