### 9.6 Sample size calculation and sample power

The primary endpoint is defined as a maximum change of 3 mmHg between the two treatments, with a power of 90%, reliability of 95%, and losses of 10%, a 1:1 ratio, and a sample size of 50:50 (1 patient = 2 study subjects).

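### The protocol names two different primary endpoints for a non-inferiority trial; the only margin and the 90% power belong to mean blood pressure, and the control proportion has neither a margin nor a decision rule

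*Protocol*

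**What the plan says.** Section 4 describes a "Randomized, controlled, 2x2 crossover, phase III, non-inferiority clinical trial". The primary endpoint is then stated in two ways.

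- **As a proportion.** The synopsis and section 3.1 set the primary objective "as measured by the proportion of patients with blood pressure control" at week 8. Section 9.3.1 agrees: "The primary efficacy endpoint will be the proportion of participants who achieve blood pressure control", with a threshold of 140/90 mmHg.
- **As a mean difference.** The sample size paragraph in section 4.2 is written "for the hypothesis of non-inferiority in blood pressure control, to an alternative tail taking a 2.5% significance level with 90% power", but its inputs are on the mmHg scale: "where a maximum change of 3.0 mmHg was taken as the maximum level of change between the two treatments in SBP and DBP", with an SD of 6 mmHg. Section 9.6 goes further: "The primary endpoint is defined as a maximum change of 3 mmHg between the two treatments, with a power of 90" percent.

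Section 9.5.1.1, headed as the primary efficacy analysis, covers both. It opens with the difference in mean SBP and DBP and its 95% CI from a crossover ANOVA. It then says that the differences in proportions "will be evaluated using McNemar's chi-square test for differences in proportions with and without continuity correction or Fisher's exact test for paired designs" when expected values are below 5. The summary in section 9.1 adds a 95% CI for the difference in proportions. Nowhere does the protocol give a margin, an expected control rate, a discordance rate or a rule for concluding non-inferiority on the proportion scale.

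**The concern.** A non-inferiority conclusion needs one endpoint, a margin on that endpoint's scale, and a rule that compares a confidence limit with the margin. Here the endpoint named as primary in the objectives has no margin. The quantity that has a margin is called primary only in the sample size section.

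McNemar's test asks whether two paired proportions are equal. Failing to reject equality in 44 to 50 patients does not show that the new product is not worse by an unacceptable amount. If the choice between the endpoints, or the margin for the proportion, is settled after the data are seen, the conclusion depends on the data. A reader of the protocol would also take the 90% power to belong to the proportion, which it does not.

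**Working it through.** **1. Reproduce the plan's sample size.** Inputs from section 4.2: margin 3 mmHg, SD of the difference 6 mmHg, one-sided 2.5%, power 90%, loss 10%, true difference taken as 0.

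- Normal approximation: n = [6 × (1.960 + 1.282) / 3]² = 42.03, so 43.
- Paired t (noncentral t): power is 0.893 at n = 43 and 0.900 at n = 44. The stated 44 is reproduced.
- Loss: 44 / 0.9 = 48.9, so 49; the protocol states 50.

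The arithmetic is sound, for one mean.

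**2. Power of the same 44 pairs for the proportion.** The protocol gives neither a margin nor a discordance rate, so both are assumed. With a true difference of 0, margin m and a fraction ψ of patients controlled on one product only, power ≈ Φ(m / √(ψ/n) − 1.96).

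| Discordance ψ | Power, m = 10 points, n = 44 | n = 50 | Pairs for 90%, m = 10 points | Margin giving 90% at n = 44 |
|---|---|---|---|---|
| 10% | 55% | 61% | 106 | 15.5 points |
| 15% | 40% | 45% | 158 | 18.9 points |
| 20% | 32% | 35% | 211 | 21.9 points |
| 30% | 23% | 25% | 316 | 26.8 points |

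The pairs needed are ψ × (1.960 + 1.282)² / m². The last column is 3.2415 × √(ψ/44).

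**3. What a non-significant McNemar result allows.** Take 44 pairs, with 8 patients controlled only on the comparator and 2 only on the test product.

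- p = 0.058 uncorrected, 0.114 with continuity correction, 0.109 exact.
- Observed difference: (2 − 8)/44 = −13.6 points. SE = √(10 − 36/44)/44 = 0.0689, so the Wald 95% CI is −27.1 to −0.1 points.

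All three p-values exceed 0.05, yet the interval reaches a 27-point deficit.

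By full enumeration, with and without the correction at 44 and 50 pairs, a product truly 10 points worse (assumed discordant splits from 12.5%/2.5% to 20%/10%) gives p < 0.05 in 14% to 45% of trials. For a 20-point deficit (22.5%/2.5% to 30%/10%) the range is 46% to 82% at 44 pairs and 53% to 87% at 50.

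**4. Fisher's test on a paired table.** With 36 patients controlled on both products, 4 on neither, and 2 and 2 discordant, the treatment difference is (2 − 2)/44 = 0. Ordinary Fisher on [[36, 2], [2, 4]] gives p = 0.0015, because it tests whether the two responses are associated within patients.

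**5. If SBP and DBP must both succeed.** Simulating the two paired-t confidence limits (SD 6 for both, true differences 0, assumed correlation 0 to 0.8) gives joint power of 81% to 86% at 44 evaluable patients and 87% to 90% at 50.

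**The case against.** The strongest reply is that the protocol already holds most of a non-inferiority framework. Section 9.5.1.1 plans a 95% CI for the difference in mean SBP and DBP under the primary analysis heading, and section 4.2 supplies the margin and a one-sided 2.5% level that matches that interval. Section 9.1 also plans a CI for the difference in proportions, which is the right tool. Both points stand. A reader might infer that the trial cannot show non-inferiority at all, or that its analysis consists only of equality tests; the documents do not support that. What is missing is a margin and rule for the proportion, and agreement on which endpoint is primary.

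Four further inferences go too far.

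- **The sample size is miscalculated.** It is not; step 1 reproduces it.
- **Any worse product would usually pass as not significantly different.** That follows for a 10-point deficit under the assumed splits. For 20 points McNemar often rejects.
- **The Fisher test is certainly wrong and would usually be used.** The wording names paired designs and may be meant as the exact McNemar test, so the text is ambiguous. The chance of the switch depends on what expected values means. If it means expected discordant cells below 5 (fewer than 10 discordant pairs), the chance at 44 pairs runs from 0.99 at 10% discordance to 0.11 at 30%.
- **The trial is underpowered for SBP and DBP jointly.** The protocol applies 3 mmHg to both components but does not say that both must succeed, and at 50 evaluable patients joint power is close to 90%.

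It might also be said that a separate analysis plan can supply the rule. But the protocol itself fixes the primary endpoint, the margin, the sample size and the test, and they contradict each other.

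**Conclusion.** The concern holds as a contradiction over the primary endpoint. The objectives and section 9.3.1 name the week-8 control proportion, while sections 4.2 and 9.6 attach the only margin, the sample size and the 90% power to mean blood pressure, and section 9.6 calls that primary. If the proportion is primary, nothing in the protocol can establish non-inferiority on it, neither the McNemar or Fisher p-value nor the planned interval, because there is no margin to read them against.

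The 90% power does not transfer to the proportion. At 44 pairs and an assumed 10-point margin it is about 55% to 23% for 10% to 30% discordance, and 90% would need a margin of about 15 to 27 points. These figures rest on assumed margins and discordance and on a true difference of zero; the contradiction itself rests on no assumption. It should be resolved before unblinding.

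**What to change.** Choose one primary endpoint and state it identically in the synopsis and sections 3.1, 4.2, 9.1, 9.3.1, 9.5.1.1 and 9.6. Either choice is defensible.

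- **(a) Means primary.** Use the treatment difference (Richmond minus comparator) in mean SBP and DBP at week 8, from the analysis already planned in section 9.5.1.1. Conclude non-inferiority if the upper limit of the two-sided 95% CI is below 3 mmHg. Say whether both components must succeed; if so, restate joint power as about 81% to 86% at 44 and 87% to 90% at 50 evaluable patients, with the assumptions in step 5. Report the control proportion as secondary, as a paired risk difference with a 95% CI.
- **(b) Proportion primary.** State and justify a margin in percentage points. Conclude non-inferiority if the lower limit of the 95% CI for the paired difference (Richmond minus comparator) lies above minus that margin. Give the assumed control and discordance rates, and replace the 90% with the power that 44 to 50 pairs deliver.

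In either case replace the Fisher wording with the exact binomial McNemar test, and choose one McNemar version in advance.

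The cost is a protocol amendment, which section 9 already requires for changes to endpoints or methods proposed during the study and before unblinding. No new data are needed. The stated power becomes less favourable under (b), and under (a) if both components must succeed; (a) also moves the sponsor's stated primary objective to secondary.
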